Continuous Glucose Monitoring System (CGMS): To evaluate the effect of blood glucose levels on eating behavior in a population of patients with diabetes in a free-living environment; we plan to study 15 lean healthy control subjects (BMI <25 kg/m²), 15 obese non-diabetic subjects (BMI > 30 kg/m²), 15 T2DM subjects who will be age and BMI-matched to obese, non-diabetic subjects, and 15 T1DM subjects who will be age and BMI matched to control, non-diabetic subjects. The participants will come to the research unit for a screening visit to review their medical history and receive a physical examination. Blood tests will be collected for exclusion of anemia (hematocrit), diabetes (A1c), untreated thyroid disease (TSH), or any other major health problems (liver enzymes and creatinine). The total amount of blood drawn will be less 1 table spoon. All female subjects will undergo a urine pregnancy test at the time of screening. These blood and urine tests will not be performed if they have been done within the 3 months prior to the screening visit. The participants who qualify will be invited to use the CGMS (DEXCOM G4 Platinum) for up to 7 days. On the visit for placement of the CGMS: 1) the participants will be explained by one of the study physicians how to use a glucometer (FreeStyle or Accu-Check), 2) they will have the CGMS inserted under the skin, and 3) they will be instructed how to fill up the food log (using informational brochures). On the second visit (up to 7 days after the initial visit) the CGMS will be removed from the skin and the glucose meter and food log will be returned to the investigators. The first visit will last approximately 1 hour and the second visit about 30 minutes. The CGMS consists of 3 parts: sensor, transmitter and monitor. The small sensor measures the glucose levels from the interstitial tissue. The transmitter is attached on top of the sensor and connects wirelessly to the monitor. The sensor is sterile and comes in an unopened package. It has a plastic wire-like tip that is placed under the skin and continuously measures the glucose levels. One of the study physicians will insert the CGMS wire-like tip under the volunteer's skin with the use of the DEXCOM sensor insertion kit. The transmitter is snapped to the sensor pod and the sensor/transmitter unit will be attached to the skin with an adhesive patch. The monitor is the size of a small hand-held device with a digital screen that displays a graph showing the glucose levels from the previous 4-24 hours. While using the CGMS, the volunteers will need to check their glucose levels with a glucose meter twice a day to calibrate the device. One of the investigators will teach the volunteers how to use the glucose meter, which will be loaned to the volunteers during the CGMS session. The monitor and transmitter should be kept 6 meters apart for adequate wireless communication. While using the CGMS the participants will be asked to fill up a food record. The Food Record will ask about amount and type of food consumed throughout the day. The participants will also register how hungry they are before the meal and how full they feel after they ate, and type and duration of physical activity. After completing the CGMS session, the sensor will be removed by one of the investigators. To remove the sensor, the adhesive patch will be gently peeled off from the skin, together with the sensor pod and transmitter. Removal of the sensor is a painless procedure. The sensor and sensor

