
pod will be discarded after use. The transmitter and receiver and glucose meter will be disinfected with a bleach solution and 70% isopropyl alcohol wipes to remove any disinfectant residue.

4. Genetic Testing N/A

A. Describe

- i. the types of future research to be conducted using the materials, specifying if immortalization of cell lines, whole exome or genome sequencing, genome wide association studies, or animal studies are planned
- ii. the plan for the collection of material or the conditions under which material will be received
- iii. the types of information about the donor/individual contributors that will be entered into a database
- iv. the methods to uphold confidentiality

B. What are the conditions or procedures for sharing of materials and/or distributing for future research projects?

C. Is widespread sharing of materials planned?

D. When and under what conditions will materials be stripped of all identifiers?

E. Can donor-subjects withdraw their materials at any time, and/or withdraw the identifiers that connect them to their materials?

- i. How will requests to withdraw materials be handled (e.g., material no longer identified: that is, anonymized) or material destroyed?

F. Describe the provisions for protection of participant privacy

G. Describe the methods for the security of storage and sharing of materials

5. Subject Population: Provide a detailed description of the types of human subjects who will be recruited into this study.

15 lean, healthy control subjects (BMI <25 kg/m²)

15 obese, non diabetic subjects (BMI > 30 kg/m²)

15 T2DM subjects who will be age and BMI-matched to obese, non-diabetic subjects

15 T1DM subjects who will be age and BMI matched to control, non-diabetic subjects.

6. Subject classification: Check off all classifications of subjects that will be specifically recruited for enrollment in the research project. Will subjects who may require additional safeguards or other considerations be enrolled in the study? If so, identify the population of subjects requiring special safeguards and provide a justification for their involvement.

 Children	 Healthy	 Fetal material, placenta, or dead fetus
 Non-English Speaking	 Prisoners	 Economically disadvantaged persons

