 Decisionally Impaired	 Employees	 Pregnant women and/or fetuses
 Yale Students	 Females of childbearing potential	

NOTE: Is this research proposal designed to enroll children who are wards of the state as potential subjects? Yes No (If yes, see Instructions section VII #4 for further requirements)

7. Inclusion/Exclusion Criteria: What are the criteria used to determine subject inclusion or exclusion?

Inclusion criteria (for both diabetic and non-diabetic participants):

- Age 18-65 years
- A1c < 10.5 %

Exclusion criteria:

BMI <18 (no upper limit), Creatinine > 1.5 mg/dL, Hgb < 10 mg/dL, ALT > 2.5 X ULN, untreated thyroid disease, uncontrolled hypertension, known neurological disorders, untreated psychiatric disorders, use of antidepressants and psychiatric medications, use of weight loss medications in the 6 months prior to the study, malignancy, smoking, current or recent steroid use in last 3 months, history of current illicit drug use; for women: pregnancy, or breastfeeding.

8. How will **eligibility be determined, and by whom?**

Eligibility will be determined by a qualified physician associated with the research protocol and will be based upon the above inclusion/exclusion criteria

9. Risks: Describe the reasonably foreseeable risks, including risks to subject privacy, discomforts, or inconveniences associated with subjects participating in the research.

The CGMS poses no major risks to the subjects. Participants may feel a mild discomfort (pin prick sensation) during the sensor insertion. Some individuals may experience black and blueness of the skin at the insertion site of the CGMS sensor, which resolves by itself in a few days. Redness and discomfort (inflammation) can occur at the sensor insertion site. Rarely sensors may fracture and a small piece may remain under the skin which will need to be removed by the physician. This may cause mild discomfort, bruising, or temporary bleeding.

Blood samples will be obtained with a needle inserted into a vein which results in mild discomfort, bruising and temporary bleeding.

10. Minimizing Risks: Describe the manner in which the above-mentioned risks will be minimized.

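### The anemia exclusion in Section V, item 7 cannot operate as printed (hemoglobin limit of 0.01 g/dL, and not the analyte screened); secondarily, no A1c definition of a non-diabetic control is written down

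*Combined protocol and SAP*

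**What the plan says.** All references are to the combined protocol and SAP.

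**Anemia.** Section V, item 7 gives the laboratory exclusions as "Creatinine > 1.5 mg/dL, Hgb < 10 mg/dL, ALT > 2.5 X ULN". Item 8 has a qualified study physician decide eligibility and says the decision "will be based upon the above inclusion/exclusion criteria". Item 3 describes the screening visit: "Blood tests will be collected for exclusion of anemia (hematocrit), diabetes (A1c", followed by thyroid, liver and kidney tests. It names no hematocrit value. The list of laboratory data in Section VIII names neither hemoglobin nor hematocrit, although it is worded as an open list.

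**A1c.** Item 7 opens with "Inclusion criteria (for both diabetic and non-diabetic participants" and, under that heading, sets a single A1c ceiling of 10.5%. Item 5 describes the control groups as "15 lean, healthy control subjects" and "15 obese, non diabetic subjects", each with a BMI limit. The diabetic groups are matched to them, for example "15 T2DM subjects who will be age and BMI-matched to obese, non-diabetic subjects". No section gives an A1c value for the control groups.

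**The concern.** Item 8 makes the item 7 list the operative eligibility rule, so a wrong threshold there is more than a background typing error. The anemia line has two separate defects. Its unit makes the limit meaningless, and its analyte is not the one that item 3 says will be measured. Correcting the unit alone would still leave the named screening test without a criterion.

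The A1c point is different in kind. The T2DM group is matched on age and BMI to the obese controls, and the T1DM group to the lean controls. Diabetes status is therefore what is meant to separate each matched pair. Item 3 assigns A1c the task of excluding diabetes, but the value that decides the question is not written down. What is at stake is whether the control groups are classified in a reproducible, documented way.

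**Working it through.** **Step 1: the unit.** The input is the hemoglobin limit in item 7, 10 mg/dL. With 1000 mg per g, 10 / 1000 = 0.01 g/dL (0.1 g/L). No volunteer could realistically fall below this, so the printed line excludes essentially no one. The creatinine limit just before it is also in mg/dL, which suggests the unit was carried over. If g/dL was intended, which is an assumption the documents do not confirm, the printed limit is too low by a factor of 10 / 0.01 = 1000.

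**Step 2: the analyte.** The places that bear on anemia, side by side:

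| Place | Analyte | Threshold |
|---|---|---|
| Section V, item 3 (screening) | hematocrit | none |
| Section V, item 7 (exclusion) | hemoglobin | 10 mg/dL |
| Section VIII (laboratory data, open list) | neither named | none |

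The test that is named has no threshold, and the threshold belongs to a test that is not named. Item 8 points only to item 7.

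**Step 3: the A1c rule.** Item 3 plans 15 T2DM and 15 T1DM subjects, so 15 + 15 = 30 of the 60 participants have diabetes by design. Excluding diabetes by A1c can therefore apply only to the other 30, the lean and obese controls. Item 3 does not say so. Compare how BMI and diabetes status are handled:

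| Characteristic | Common rule (item 7) | Group rule (items 3 and 5) |
|---|---|---|
| BMI | "BMI <18 (no upper limit" | below 25 for lean, above 30 for obese |
| Diabetes status | A1c below 10.5% | words only; no A1c value |

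BMI has a common rule and then numerical group limits. Diabetes status has a common rule and a label. The 10.5% ceiling does not conflict with a stricter control-group rule; that rule is simply not stated. It is the only A1c number in the document.

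The anemia limit and the A1c ceiling are typed thresholds, not derived figures, so there is no calculation in the plan to reproduce.

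**The case against.** The strongest case against the point is that a competent screening physician would meet neither problem in practice. The hemoglobin unit is an obvious slip. Item 3 sits under a form instruction asking for non-technical language, so hematocrit may be a loose name for the anemia test. The study is a pilot, and item 7 leaves other conditions, such as uncontrolled hypertension, without numbers. Most of this stands and is why the severity is minor. It does not remove the defect, because the operative list still carries a wrong limit and an analyte that does not match the screening description.

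On A1c, a reader might infer that the protocol admits people with diabetes as controls provided their A1c is below 10.5%. The documents do not support that. Item 3 draws A1c to exclude diabetes and takes a medical history. Item 5 requires healthy lean and non-diabetic obese controls. Section VII, item 6 describes checking clinic patients' records for a diabetes diagnosis before contact. The intention is clear, and known diabetes is not at issue. What remains is undiagnosed diabetes seen on a screening A1c, where the physician must supply the cut-off.

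A reader might also want to convert this gap into lost power. The documents give no basis for it. The number of misclassified controls is unknown and may be 0, and how such a person would respond is unknown. The power statement in item 12 is a floor for a main effect of group across glycemic conditions, not a point value for one matched comparison.

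**Conclusion.** The anemia exclusion is wrong as written. Its limit equals 0.01 g/dL, and it names hemoglobin where the screening description names hematocrit without a threshold. This rests on the text and one unit conversion, and confidence in it is high. That the unit is a slip is an inference. No effect on a group comparison is claimed, and none can be shown from the documents.

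The A1c point holds only as a gap in specification. The 10.5% ceiling is a valid common upper bound, the intention to keep diabetes out of the control groups is stated, and the missing item is the value that defines it. That different physicians would classify the same result differently is possible but conjectural.

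Overall severity is minor.

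**What to change.** 1. The investigator should correct the hemoglobin unit in Section V, item 7, and reconcile items 3 and 7 so that one anemia analyte, with its threshold, appears in both. No threshold is proposed here.
2. The investigator should state the A1c-based definition of non-diabetic for the lean and obese control groups, in item 5 beside the BMI limits or in item 7. Item 3 should say that the diabetes exclusion applies only to those two groups. The common A1c ceiling can stay as it is.

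The cost is a short wording amendment. A1c and an anemia test are already part of screening, so no new type of test is needed, and the sample size and analysis do not change.

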- I have read a copy of the protocol and approve it being conducted at YNHH.
- I agree to notify the IRB if I am aware of any real or apparent institutional conflict of interest.
- The principal investigator of this study is qualified to serve as P.I. and has the support of the hospital for this research project.

YNHH HSPA Name (PRINT) and Signature

Date

For HIC Use Only

Date Approved

Human Investigation Committee Signature

This protocol is valid through _____

SECTION V: RESEARCH PLAN

1. Statement of Purpose: State the scientific aim(s) of the study, or the hypotheses to be tested.

To investigate whether the daily glucose profiles as assessed by continuous glucose monitoring for 1 week of normal weight, obese, and diabetic individuals relate to hunger levels and food intake.

2. Background: Describe the background information that led to the plan for this project. Provide references to support the expectation of obtaining useful scientific data.

The rising incidence of type 2 diabetes (T2DM) and obesity has paralleled the increased consumption of sugar, which has been associated with numerous adverse metabolic effects including weight gain, insulin resistance, cognitive decline, and stroke ¹⁻³.

Human studies using nuclear magnetic resonance spectroscopy (MRS), a powerful, non-invasive tool to determine the concentration of metabolites in living tissue, have shown that glucose transport across the BBB is not rate limiting during hyperglycemia ^{4,5}. Furthermore, in previous

work from our lab, brain glucose levels remain elevated in chronically hyperglycemic diabetic rats suggesting that there is very limited protective adaptation by the BBB⁶. We have also shown using microdialysis probes and hyperglycemic clamp in human subjects undergoing electrophysiological evaluation for epilepsy that brain microdialysate from non-epileptogenic brain areas showed a 200% rise in glucose levels from baseline during a hyperglycemic clamp⁷.

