Furthermore, previous published data from our lab¹³, subjects using a 2-step clamp, i.e. euglycemia (~90 mg/dL) followed by mild hypoglycemia (~65 mg/dL) in conjunction with fMRI and visual stimuli of food/non-food, showed that euglycemia was associated with activation of prefrontal cortex (PFC) and anterior cingulate ($p < 0.05$), while during hypoglycemia there was activation of hypothalamus, nucleus accumbens, insula, caudate and putamen in response to visual food cues ($p < 0.05$). In addition, hunger was increased during hypoglycemia as compared to the euglycemic phase (5.7 ± 0.5 vs 4.5 ± 0.5 ; $p < 0.01$). The study also included a small group of obese subjects ($n=5$). When this group was compared to lean subjects, they failed to show activation of the medial pre-frontal cortex during euglycemia and showed greater bilateral activation of the hypothalamus, striatum and insula in response to high-calorie food images during mild hypoglycemia ($p < 0.05$). Taken together the data suggest that during euglycemic phase of the clamp study there was activation of PFC in lean individuals, a region involved in complex cognitive behaviors, decision making and moderating correct social behavior¹⁴, whereas during hypoglycemic phase limbic regions were activated; which are involved in physiological and emotional responses¹⁵. Of particular interest these preliminary data suggest that the neural response to food consumption and food cues is altered in obese individuals in a way that could contribute to overeating behavior, namely increased stimulation of reward centers in response to nutrients (glucose) and/or food cues. This differentiated brain response could be a contributing factor to the pathogenesis of human obesity. We also plan to study patients with diabetes, who have chronic high glucose levels. Preliminary work from our group showed that obese unlike lean subjects suppressed activity in the ventral medial PFC (executive-control area) in response to food images; with a preferential liking/wanting for high-calorie food during hyperglycemia¹⁶. Therefore, we want to investigate if changes in circulating glucose levels can interfere with eating behavior and food intake in lean, obese subjects and patients with diabetes.

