Continuous glucose monitoring (CGM) is used in people with diabetes for better glycemic control as well as in non-diabetic individuals to characterize glucose patterns¹⁷⁻¹⁹. No study thus far has looked into glucose profiles normal weight, obese, and diabetic individuals in a normal, outpatient setting in relation to hunger and food intake. In a preliminary study of 8 individuals who wore a CGMS for 1 week and recorded their food intake and hunger levels, we found that increasing subjective hunger levels are more related to pre-prandial glucose peaks as opposed to nadirs. Furthermore, declines in glucose are correlated with caloric intake as well as the

macronutrient content of subsequent meals. Our findings suggest that glycemic excursions following a meal may play a role in hunger and food choices for the subsequent meal.

3. Research Plan: Summarize the study design and research procedures using non-technical language that can be readily understood by someone outside the discipline. Be sure to distinguish between standard of care vs. research procedures when applicable, and include any flowcharts of visits specifying their individual times and lengths. Describe the setting in which the research will take place.

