This is a pilot project. We estimate that a sample size of 15 subjects per group will provide 80% power to detect within group differences of 1.1 standard deviations. For changes in hunger ratings of liking, wanting and hunger we will have at least 80% power to detect between group differences across all glycemic conditions (i.e. main effect of group) of 1.0 standard deviation and within each condition of 1.25 standard deviations.

SECTION VI: RESEARCH INVOLVING DRUGS, BIOLOGICS, RADIOTRACERS, PLACEBOS AND DEVICES

N/A

A. DRUGS, BIOLOGICS and RADIOTRACERS

1. **Identification of Drug, Biologic or Radiotracer:** What is (are) the **name(s)** of the drug(s) biologic(s) or radiotracer(s) being used? Identify whether FDA approval has been granted and for what indication(s).

All protocols which utilize a drug, biologic or radiotracer **not** approved by, but regulated by, the FDA, or a radiotracer regulated by the RDRC, must provide the following information:

- a. What is the Investigational New Drug (IND) **number** assigned by the FDA?
- b. Who holds the IND?
- c. All protocols which utilize a radiotracer not approved by, but regulated by the FDA must provide the IND number: _____
Alternatively, use of the investigational radiotracer may be under RDRC/RSC oversight: (check if appropriate) _____

For all investigational radiotracers, attach a copy of the RDRC/RSC application (for radioisotopes used in the PET Center, PET Center personnel may complete this step)
Go to <http://rsc.med.yale.edu/login.asp?url=myApps.asp>. When you have logged in, complete the application and attach a copy to this submission.

Alternatively, an **exemption from IND filing requirements** may be sought for a clinical investigation of a drug product that is lawfully marketed in the United States. If there is no IND and an exemption is being sought, review the following categories and complete the category that applies (*and delete the inapplicable categories*):

Exempt Category 1

The clinical investigation of a drug product that is lawfully marketed in the United States can be exempt from IND regulations if all of the following are yes:

- i. The intention of the investigation is NOT to report to the FDA as a well-controlled study in support of a new indication for use or to be used to support any other significant change in the labeling for the drug. Yes No

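### Section V, item 12 states power for ratings and glycemic conditions that the CGM week does not define, and gives no analysis of how glucose relates to hunger and food intake

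*Combined protocol and SAP*

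**What the plan says.** Section V, item 12 (Statistical Considerations) is the only statistical text. It calls the study a pilot, sets 15 participants per group, and gives three figures:

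- "80% power to detect within group differences of 1.1 standard deviations", with no outcome or contrast named.
- "For changes in hunger ratings of liking, wanting and hunger", at least 80% power for "between group differences across all glycemic conditions (i.e. main effect of group) of 1.0 standard deviation".
- For the same ratings, at least 80% power "within each condition of 1.25 standard deviations".

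Item 12 states no alpha, sidedness, test, number of conditions, within-person correlation or multiplicity rule.

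The aim in item 1 (Statement of Purpose) is whether one week of CGM glucose profiles in normal weight, "obese, and diabetic individuals relate to hunger levels and food intake".

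Item 3 (Research Plan) describes four groups of 15 (60 in all, matching the enrolment target in Section VII), each wearing a CGM at home for up to 7 days. Participants record what and how much they eat, hunger before meals, fullness afterwards, and physical activity.

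**The concern.** Item 12 treats glycemic condition as a factor separate from group: there is a main effect of group over all conditions, and a group difference inside each one. Nothing in item 3 creates such a factor. Glucose is not set at any level, and no rule sorts CGM readings or meals into conditions. Liking and wanting are powered, but no such rating is described. A reader cannot tell which comparison in this study has the claimed power.

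The second gap matters more. A group comparison of pre-meal hunger can be run, but it does not ask whether glucose relates to hunger or intake. Item 12 names no glucose summary, no model for that relation and no handling of repeated meals, and it omits food intake. With the exposure left open, it can be chosen after the data are seen. The preliminary study of 8 people in item 2 (Background) already weighed one glucose feature against another for hunger: "increasing subjective hunger levels are more related to pre-prandial glucose peaks as opposed to nadirs". It linked a third feature, the decline in glucose, to caloric intake and the make-up of the next meal.

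**Working it through.** **1. Item 12 against item 3**

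| Element in item 12 | In the CGM week (item 3)? | Elsewhere in the protocol |
|---|---|---|
| Several glycemic conditions | Not imposed, not derived from the trace | Background only: "subjects using a 2-step clamp, i.e. euglycemia (~90 mg/dL) followed by mild hypoglycemia (~65 mg/dL" |
| Liking, wanting | No rating described | Background only: "preferential liking/wanting for high-calorie food during hyperglycemia" |
| Hunger | Yes, before meals | Aim (item 1) |
| Within-group difference | No outcome or contrast named | None |
| Food intake | Collected, but absent from item 12 | Aim (item 1) |
| Glucose against hunger or intake | No analysis named | Preliminary correlations in item 2 |

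**2. Can the three figures be reproduced?**

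From the protocol: n = 15 per group, four groups, and 1.1, 1.0 and 1.25 SD. Assumed, because not stated: two-sided 0.05 unless noted, and noncentral t or F power. The figures cannot be reproduced from stated inputs alone, but each can be reached.

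*Within group, 1.1 SD.* Paired t, df = 14, noncentrality = d × √15.
- If 1.1 is in SDs of the difference: power 97.7%.
- If 1.1 is in SDs of a single measurement with zero within-person correlation, the SD of the difference is √2 times larger. Then d = 1.1/√2 = 0.778 and power is 80.0%.

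*Between groups within a condition, 1.25 SD.* Two-sample t, df = 28, noncentrality = d × √(15/2) = 1.25 × 2.739 = 3.42.
- Alpha 0.05: 91.0%.
- Alpha 0.05/3: 80.3%.
- Four-group ANOVA, two means 1.25 SD apart and the other two midway: noncentrality = 15 × 1.25²/2 = 11.72, df 3 and 56, power 80.1%.

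*Between groups over all conditions, 1.0 SD.* Averaging k conditions with correlation ρ multiplies the SD by √((1+(k−1)ρ)/k).
- k = 2, ρ = 0.5: factor 0.866, effective d = 1.155, power 86.3%.
- k = 3, ρ = 0.8: factor 0.931, effective d = 1.074, power 81.1%.

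Reaching each figure needs a choice of SD, test, alpha or number of conditions that the text does not make.

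**3. What 1.0 SD means if the conditions are dropped (illustration only)**

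| Reading of 1.0 SD, 15 per group | Power |
|---|---|
| SD of the one value per person; unadjusted two-group t-test (noncentrality 2.739) | 75.3% (80% needs 1.06 SD) |
| SD of a single rating; person mean over 21 assumed meals, ρ = 0.8 (factor 0.900, d = 1.111) | 83.6% |
| Same, ρ = 0.5 (factor 0.724, d = 1.382) | 95.5% |

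The choice of test also matters. At 1.06 SD, where the unadjusted t-test has 80% power, a four-group ANOVA with the two extreme means that far apart and the others midway has 64.5% (noncentrality 15 × 1.06²/2 = 8.43). The number of meals and the correlations are assumptions; the protocol gives neither.

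**The case against.** Three objections deserve weight.

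*This is a pilot, and formal power is optional.* That is fair as far as it goes, and a gap between 75% and 80% would be immaterial in a pilot. But the protocol chose to state power, and the statement refers to things it does not define. A pilot also still needs an analysis of its own question.

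*Conditions could be derived from the CGM trace, and liking and wanting might be on the food log.* Both are possible. The log and its instruction brochures are not in the documents, so it can be said only that the protocol describes no such rating and no rule for forming conditions. The fix leaves both routes open.

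*The figures may be sound.* This stands. A reader might infer that 1.1 SD betrays a different contrast or a stricter alpha, since a paired test has 97.7% power if the SD is that of the difference. The documents do not support that: the same test at 0.05 gives 80.0% in single-measurement SD units at zero correlation. A reader might also infer that deleting the conditions breaks the 80% claim at 1.0 SD. It does so only if 1.0 is the SD of the person-level value; averaging over meals can keep power above 80%. Nor is 75% or 1.06 SD the correct replacement, because both rest on an assumed unadjusted pairwise t-test in a four-group study.

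It is also fair to say that the peak and the decline reported in item 2 are not rivals for one outcome: the first is linked to hunger, the second to intake. That makes it easy to fix one exposure per outcome, which the plan has not done.

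**Conclusion.** The point holds as a mismatch and an omission. The power in item 12 belongs to a design with glycemic conditions and with liking and wanting ratings, and item 3 describes neither. The aim in item 1 has no stated analysis. Both conclusions come from reading the sections side by side and need no assumed number.

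The numerical size cannot be fixed from the documents. Under assumed two-sided 0.05 tests, the 1.0 SD claim corresponds to anything from 75.3% to 95.5% power across the readings tabulated above. That spread shows how little the sentence pins down; it does not show that the original calculation was wrong. The wording resembles the earlier experiments described in item 2, and a reader might infer that it was carried over from them, but the documents do not say where it came from.

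Item 12 should be corrected before the data are analysed, chiefly so that the study's own question has an analysis fixed in advance.

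**What to change.** 1. **Rewrite item 12 to match item 3.** Remove liking, wanting and the condition-based figures, or define them from data the study collects. For every figure kept, including 1.1 SD, state the outcome, the contrast, which SD is meant (single rating or person mean), the test and the alpha, then recompute the power. Keep the pilot label, 15 per group and the group comparison of pre-meal hunger. The investigators should supply the replacement figures from their own inputs.

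2. **Pre-specify one analysis of the aim.** It should respect repeated meals within a person and fix the glucose exposure for each outcome in advance, for example the pre-prandial peak for hunger and the pre-meal decline for intake, following the preliminary findings in item 2. A meal-level mixed model with a participant random effect and a group-by-glucose term would suit, provided the food log records meal times; that needs checking.

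The cost is rewording, modest analysis work, a check of the food log, and possibly a less favourable stated power figure. No additional participants or visits are required.
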